12.1 Overview

This section defines the types of safety data that will be collected under this protocol and outlines the procedures for appropriately collecting, grading, recording, and reporting those data. Adverse events that are classified as serious according to the definition of health authorities must be reported promptly (per Section 12.5, Reporting of Serious Adverse Events and Adverse Events) to DAIT/NIAID. Appropriate notifications will also be made to site principal investigators, Institutional Review Boards and health authorities.

Information in this section complies with ICH Guideline E2A: Clinical Safety Data Management: Definitions and Standards for Expedited Reporting, ICH Guideline E-6: Guideline for Good Clinical Practice, 21CFR Parts 312 and 320, and applies the standards set forth in the National Cancer Institute (NCI), Common Terminology Criteria for Adverse Events (CTCAE), Version 5.0 : <http://ctep.cancer.gov/reporting/ctc.html>.

12.2 Definitions

12.2.1 Adverse Event (AE)

Any untoward or unfavorable medical occurrence associated with the subject's participation in the research, whether or not considered related to the subject's participation in the research (modified from the definition of adverse events in the 1996 International Conference on Harmonization E-6 Guidelines for Good Clinical Practice) (from OHRP "Guidance on Reviewing and Reporting Unanticipated Problems Involving Risks to Subjects or Others and Adverse Events (1/15/07)" <http://www.hhs.gov/ohrp/policy/advevntguid.html#Q2>)

For this study, an adverse event will include any untoward or unfavorable medical occurrence associated with:

- **Study vaccine regimen:** Shingrix® will be administered 0.5mL intramuscularly on Day 0 and Day 60. Solicited AEs will be collected beginning from each vaccination though Day 7, unsolicited AEs will be collected through 30 days after each vaccination. Serious adverse events will be collected through the completion of the study.

- **Study mandated procedures:** Adverse events associated with intramuscular injections or blood draws will be collected for 24 hours after study-mandated injections and phlebotomies.

12.2.1.1 Suspected Adverse Reaction (SAR)

Any adverse event for which there is a reasonable possibility that the investigational drug caused the adverse event. For the purposes of safety reporting, 'reasonable possibility' means there is evidence to suggest a causal relationship between the drug and the adverse event. A suspected adverse reaction implies a lesser degree of certainty about causality than adverse reaction, which means any adverse event caused by a drug (21 CFR 312.32(a)).

12.2.2 Unexpected Adverse Event

An adverse event or suspected adverse reaction is considered "unexpected" if it is not listed in the package insert or is not listed at the specificity, severity or rate of occurrence that has been observed.

12.2.3 Serious Adverse Event (SAE)

An adverse event or suspected adverse reaction is considered "serious" if, in the view of either the investigator or Sponsor (DAIT/NIAID), it results in any of the following outcomes (21 CFR 312.32(a)):

1. Death.
2. A life-threatening event: An AE or SAR is considered "life-threatening" if, in the view of either the investigator or Sponsor (DAIT/NIAID), its occurrence places the subject at immediate risk of death. It does not include an AE or SAR that, had it occurred in a more severe form, might have caused death.
3. Inpatient hospitalization or prolongation of existing hospitalization.
4. Persistent or significant incapacity or substantial disruption of the ability to conduct normal life functions.
5. Congenital anomaly or birth defect.
6. Important medical events that may not result in death, be life threatening, or require hospitalization may be considered serious when, based upon appropriate medical judgment, they may jeopardize the subject and may require medical or surgical intervention to prevent one of the outcomes listed above.

Elective hospitalizations or hospital admissions for the purpose of conduct of protocol mandated procedures are not to be reported as an SAE unless hospitalization is prolonged due to complications.

12.3 Grading and Attribution of Adverse Events

12.3.1 Grading Criteria

The study site will grade the severity of adverse events experienced by the study subjects according to the criteria set forth in the National Cancer Institute's Common Terminology Criteria for Adverse Events (CTCAE) (version 5.0). This document (referred to herein as the NCI-CTCAE manual) provides a common language to describe levels of severity, to analyze and interpret data, and to articulate the clinical significance of all adverse

events. The NCI-CTCAE has been reviewed by the Principal Investigator and has been deemed appropriate for the subject population to be studied in this protocol.

Adverse events will be graded on a scale from 1 to 5 according to the following standards in the NCI-CTCAE manual version 5.0:

Grade 1 = mild adverse event.

Grade 2 = moderate adverse event.

Grade 3 = severe and undesirable adverse event.

Grade 4 = life-threatening or disabling adverse event.

Grade 5 = death.

Events grade 1 or higher will be recorded on the appropriate AE case report form paper CRF for this study.

For grading an abnormal value or result of a clinical evaluation, a treatment-emergent adverse event is defined as an increase in grade from baseline or from the last post-baseline value that doesn't meet grading criteria. Changes in grade from screening to baseline will also be recorded as adverse events, but are not treatment-emergent. If a specific event or result from a given clinical or laboratory evaluation is not included in the NCI-CTCAE manual, then an abnormal result would be considered an adverse event if changes in therapy or monitoring are implemented as a result of the event/result.

12.3.2 Attribution Definitions

The relationship, or attribution, of an adverse event to the study therapy regimen or study procedure(s) will initially be determined by the site investigator and recorded on the appropriate AE paper case report form (AE/SAE paper CRF). Final determination of attribution for safety reporting will be determined by DAIT/NIAID. The relationship of an adverse event to study therapy regimen or procedures will be determined using the descriptors and definitions provided in Table 12.3.2.

For additional information and a printable version of the NCI-CTCAE manual version 5.0, consult the NCI-CTCAE web site: <http://ctep.cancer.gov/reporting/ctc.html>.

Table 12.3.2 Attribution of Adverse Events

Code	Descriptor	Relationship (to primary investigational product and/or other concurrent mandated study therapy or study procedure)
UNRELATED CATEGORY		
1	Unrelated	The adverse event is clearly not related: there is insufficient evidence to suggest a causal relationship.
RELATED CATEGORIES		
2	Possible	The adverse event has a reasonable possibility to be related; there is evidence to suggest a causal relationship.

3	Definite	The adverse event is clearly related.
---	----------	---------------------------------------

12.4 Collection and Recording of Adverse Events

12.4.1 Collection Period

Adverse events will be collected from the time of vaccination until 30 days after each vaccination or after the participant prematurely withdraws (without withdrawing consent) or is withdrawn from the study. SAEs will be collected until a participant completes the study.

12.4.2 Collecting Adverse Events

Adverse events (including SAEs) may be discovered through any of these methods:

- Observing the subject.
- Interviewing the subject and using the memory aid.
- Receiving an unsolicited complaint from the subject.

12.4.3 Recording Adverse Events

Throughout the study, the investigator will record adverse events and SAEs as described previously (Section 12.2, Definitions) on the appropriate paper case report form (AE/SAE paper CRF) regardless of the relationship to study therapy regimen or study procedure.

Once recorded, an AE/SAE will be followed until it resolves with or without sequelae, or until the end of study participation, or until 30 days after the subject prematurely withdraws (without withdrawing consent)/or is withdrawn from the study, whichever occurs first.

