7.4. Rescue Medications

Should an anaphylactic or hypersensitivity reaction occur, epinephrine (1:1000) and diphenhydramine intramuscular injections are readily available at clinic sites. If needed, the site will initiate emergency procedures as per their institution policy. If needed, participant will be transferred to the Emory University Hospital Emergency Department.

8. Study Procedures

Shingrix® vaccine will be administered in two doses (0.5 mL each, at D0 and D60) intramuscularly in the deltoid region of the arm. Aseptic technique will be used.

Blood will be drawn at D0 (pre-vaccination), and at D1, D3, D7, D14, D30, D60, D61, D63, D67, D74, D90 D180 and optional D270+ post vaccination. Stool will be collected at baseline D0 (pre-vaccination).

A targeted physical examination will be performed when deemed necessary.

A memory aid will be completed for symptom assessment (local and systemic) from Day 0 to Day 7 and from D60 to D67.

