8.1. Enrollment

The research study will be explained in lay terms to each potential research participant. The potential participant will sign an informed consent form before undergoing any study procedures. Once the informed consent has been signed, the participant is considered enrolled in the study and will be assigned a unique participant number.

Enrollment will be completed within 18 months. The duration of participation for each subject is 6 months, with an optional visit at 9 months and beyond after the first visit.

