11.4. Follow-up after Early Study Withdrawal

If a participant is withdrawn from the study for any reason, the participant may be asked to complete a final visit and/or final assessments. At this visit, study personnel may review the memory aid with the subject (if within 7 days of vaccination) review the vaccination site, list of medications, and note any other AEs or SAEs since last visit. Blood may be drawn. Physical examination will be performed only if indicated, based on review of health status. Subjects will be also asked to report local and systemic AEs and any blood draw-related AEs. These visits will last about 1 hour.

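### Safety rules for participants who withdraw are unclear on follow-up, limit late memory-aid review, and leave early leavers outside the only defined analysis set

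*Combined protocol and SAP*

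**What the plan says.** **Follow-up of recorded events.** Under Section 12.4.3, an AE or SAE already on the case report form is followed until it resolves, "or until the end of study participation, or until 30 days after the subject prematurely withdraws". The last limb covers those who leave "without withdrawing consent)/or is withdrawn from the study, whichever occurs first". Section 8.1 says "The duration of participation for each subject is 6 months", plus an optional later visit, while the study-duration line of the synopsis counts 9 months of participation. Neither says when participation ends for someone who withdraws.

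**Collection of events.** Section 12.4.1 collects AEs "until 30 days after each vaccination or after the participant prematurely withdraws". For serious events it says only that "SAEs will be collected until a participant completes the study".

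**The final visit.** Under Section 11.4, "the participant may be asked to complete a final visit and/or final assessments". At that visit "study personnel may review the memory aid with the subject (if within 7 days of vaccination"). The early-termination paragraph of Section 8.5 has the same condition. Both also provide for noting other AEs and SAEs since the last visit and for asking about local and systemic AEs, without a day limit. Section 8 gives the diary period: "A memory aid will be completed for symptom assessment (local and systemic) from Day 0 to Day 7 and from D60 to D67".

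**Analysis.** Section 13.4.1 defines one analysis set: subjects who received at least the first dose and have measurements at Day 0 and Day 30. Section 13.4.4 tabulates AE rates and compares groups by Fisher's exact test, but names no denominator. No safety population is defined.

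**The concern.** Safety is the only secondary objective, and the secondary endpoint compares related AEs and SAEs between doses. People who leave early may differ from those who stay in how they tolerated the vaccine, so the rules for them need to be explicit. Three things could go wrong. Staff could close an unresolved event at withdrawal, although the same sentence names a further 30 days. A completed diary could go unreviewed because the final visit fell after day 7. And a participant who received dose 1 but has no Day 30 measurement could be left out of the AE tables altogether, taking both their events and their place in the denominator. Section 11.3 does not replace such a participant.

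**Working it through.** The plan has no figure to reproduce here; the check applies its rules to a participant who withdraws on day w without withdrawing consent.

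**1. Follow-up of an unresolved, recorded event (12.4.3).** The rule is: end = min(end of participation, w + 30).

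- Reading A, participation ends at withdrawal: min(w, w + 30) = w. The 30-day limb never operates.
- Reading B, participation ends at the planned six months, about D180: min(180, w + 30) = w + 30 whenever w ≤ 180 − 30 = 150.

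| Withdrawal day | Reading A | Reading B |
|---|---|---|
| D10 | D10 | D40 |
| D61 | D61 | D91 |
| D160 | D160 | D180 |

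If participation is the 9 months of the synopsis, about D270, the limit in Reading B moves to 270 − 30 = D240. Reading B gives every clause effect and is probably intended, but no section says so.

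**2. Collection (12.4.1).** The 30 days may govern both halves of the phrase or only the first. For withdrawal on D10, AE collection could stop at D10 or run to D40. For SAEs the only end point is completion, which a withdrawn participant does not reach. Section 12.2.1 likewise refers only to completion of the study. Section 12.4.3 does not fill this gap, because it concerns events already recorded.

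**3. Memory aid.** The diary runs from D0 to D7 and the early-termination condition is also 7 days, so no diary day lies outside the condition. But a complete diary then exists only on the last permitted day. Set beside other rules, the limit is inconsistent:

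- The routine D7 review has a window of plus or minus 1 day (8.4.1, 8.6), so review on D8 is acceptable for someone who stays.
- The unscheduled visit (8.5) allows memory-aid review with no day limit.
- Appendix D schedules no review at D14 or D30 to catch up a missed D7 review, and has no column for the final visit.

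Take a participant reviewed on D3 who misses D7 and has a final visit on D10. Diary days D4 to D7, that is 7 − 3 = 4 days, have no review provided for.

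**4. Analysis set (13.4.1, 13.4.4).** If k of 60 dosed participants lack Day 30 data, and y of the x participants with an event are among them, the rate becomes (x − y)/(60 − k) instead of x/60. As an illustration only, with assumed x = 4 and k = 3, the full rate is 4/60 = 6.7%, and:

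| y | Rate with leavers excluded |
|---|---|
| 0 | 4/57 = 7.0% |
| 1 | 3/57 = 5.3% |
| 2 | 2/57 = 3.5% |
| 3 | 1/57 = 1.8% |

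The direction depends on who leaves. For scale, Section 5.1 gives Grade 3 rates of 1.4% to 2.4% per symptom after dose 1. If these applied here, 60 participants would yield 60 × 0.014 = 0.84 to 60 × 0.024 = 1.44 cases per symptom, so one excluded participant could decide whether a symptom appears in the table. These are background rates and do not measure a loss.

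**The case against.** Much of the case on the other side stands. Section 12.4.3 governs the later course of events already recorded; even on Reading A the event and its grade remain, and only the outcome may be missing. Early reactions have several routes into the record: memory-aid and injection-site review on D1, D3 and D7 (8.4.1), the instruction to telephone about severe reactions (8.3) and about Grade 3 reactogenicity within a week (Appendix D), and AE questioning at the final visit without a day limit. A Grade 3 reaction on D2 in someone who attends D3 would therefore be picked up. The 7-day wording is permissive, and Section 12.4.2 allows interview with the memory aid at any time.

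A reader might infer that follow-up definitely stops at withdrawal and that safety data are lost in those who leave because of a reaction. The documents do not support that. The first part depends on an undefined term whose other reading is the more coherent. The second assumes a link between reactions and departure: Section 6.5 lists severe allergic reaction as a reason to discontinue vaccine, which is separate from the reasons for leaving the study in Section 11.2. After withdrawal of consent, which in Section 11.2 includes follow-up, no wording recovers later data. Nor can a fall such as 6.7% to 3.5% be attributed to the follow-up or diary rules, which remove nobody from the count; only the analysis set could do that.

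One may also argue that Section 13.4.1 was written for the immune data. That is plausible, but it is the only population defined, and the text applies it to the data analysis without exception.

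**Conclusion.** The concern holds in a limited form. The wording of 12.4.1 and 12.4.3 is mainly a matter for clarification: it leaves staff to choose between no follow-up and 30 days of follow-up after withdrawal, and it gives SAE collection no end point for those who do not complete. Two defects are more concrete. The stated diary condition at early termination does not cover a late review that the unscheduled visit permits. And the only defined analysis set, read as written, excludes from the AE tables anyone without Day 30 measurements, whether they left or merely missed that visit.

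The size of any loss cannot be computed, because the documents give no expected number of withdrawals. Apart from the analysis-set exclusion, what is at risk is the outcome of a recorded event and a few unreviewed diary days. The conclusion assumes participants who withdraw, or are withdrawn, without withdrawing consent, and that Section 13.4.1 applies to the safety analysis because nothing else is specified.

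**What to change.** - **Sections 13.4.1 and 13.4.4:** define a safety population and compute AE rates after each dose over everyone who received that dose, regardless of Day 30 data.
- **Sections 8.5 and 11.4:** remove the 7-day limit on memory-aid review at the termination visit whenever the D0 to D7 or D60 to D67 diary has not been fully reviewed.
- **Sections 12.4.1 and 12.4.3:** reconcile them so that, for participants who withdraw or are withdrawn without withdrawing consent, the 30-day period after withdrawal applies to both AEs and SAEs, with follow-up of a recorded event ending earlier if it resolves. Apply the end-of-participation limit to completers only, and define it.

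The cost is protocol wording, a little more analysis, and about one telephone contact for each consenting withdrawn participant. The diary is already completed at home.

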12.5 Reporting of Serious Adverse Events and Adverse Events

12.5.1 Reporting of Serious Adverse Events to DAIT/NIAID

This section describes the responsibilities of the site investigator to report serious adverse events to the DAIT/NIAID Medical Monitor and Project Manager. Timely reporting of adverse events is required by 21 CFR and ICH E6 guidelines.

Site investigators will report all serious adverse events via email to the DAIT/NIAID Medical Monitor and Project Manager (see Section 12.2.3, Serious Adverse Event), regardless of relationship or expectedness, within 24 hours of discovering the event.

For SAEs, all requested information on the SAE paper CRF will be provided. Unavailable details of the event will not delay submission of the known information. As additional details become available, the SAE paper CRF will be updated and re-submitted.

12.5.2 Reporting to the FDA

Not applicable – this study is not conducted under an IND/IDE.

12.5.3 Reporting of Adverse Events to IRBs/IECs and to VAERS

The Protocol Chair shall report adverse events, including expedited reports, in a timely fashion to the IRB in accordance with applicable regulations and guidelines. Since this is an FDA-approved vaccine, vaccine-related

adverse events will also be reported to VAERS at <https://vaers.hhs.gov/index>, in accordance to VAERS guidelines.

12.6 Pregnancy Reporting

Not applicable.

12.7 Reporting of Other Safety Information

An investigator shall promptly notify the site IRB as well as the DAIT/NIAID when an “unanticipated problem involving risks to subjects or others” is identified, which is not otherwise reportable as an adverse event.

12.8 Review of Safety Information

12.8.1 Medical Monitor Review

The DAIT/NIAID Medical Monitor shall review and make decisions on the disposition of all SAEs received from the protocol investigator (See Sections 12.5.1, Reporting of Serious Adverse Events to DAIT/NIAID).

In addition to receiving individual SAE reports within 24 hours, the DAIT/NIAID Medical Monitor and Project Manager shall receive quarterly reports from the protocol investigator compiling new and accumulating information on AEs and SAEs recorded by the study site on appropriate paper CRFs.

12.8.2 Independent Safety Monitor (ISM) Review

12.8.2.1 Planned Reviews

The Independent Safety Monitor shall review safety data at least yearly. Data for the planned safety reviews will include, at a minimum, a listing of all reported AEs and SAEs.

The ISM will be informed of an Expedited Safety Report by the Protocol Chair and the DAIT/NIAID Medical Monitor in a timely manner.

12.8.2.2 *Ad hoc* ISM Reviews

In addition to the pre-scheduled planned safety monitoring, the ISM may be called upon by the DAIT/NIAID Medical Monitor for *ad hoc* reviews. The ISM will review event(s) that potentially impact(s) safety at the request of the Protocol Chair or DAIT/NIAID. In addition, the following events will trigger an *ad hoc* comprehensive ISM Safety Review:

A death of a participant, which is possibly or definitely related to the study vaccine (also a study hold - enrollment and vaccine dosing- rule)

The occurrence of one study vaccine-related and unexpected SAE or Grade 4 AE (also a study hold – enrollment and vaccine dosing- rule)

The occurrence of a Grade 3 or higher vaccine-related and unexpected SAE in 2 or more of the study participants

After review of the data, the ISM will make recommendations regarding study conduct and/or continuation.

13. Statistical Considerations and Analytical Plan

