4.4. Selection of Clinical Sites/Labs

The study will be conducted at The Hope Clinic, the clinical arm of the Emory Vaccine Center at Emory University.

Address:

[name]
[name]

Samples may be processed at the following laboratories:

[name], Stanford University, California
[name], La Jolla Institute, California
[name], Emory University, Atlanta, GA

5. Known and Potential Risks and Benefits to Participants

5.1. Risks of Investigational Product or Intervention as cited in Investigator Brochure or Package Insert

In clinical trials involving a pooled cohort of 29,305 subjects above 50 years of age who received at least one dose of Shingrix[®] (n=14,645) or saline (n=14,660) administered to a 0- and 2-month schedule, the following adverse reactions have been seen:

- Local adverse events: pain (78%), redness (38.1%), swelling (25.9%)

- General adverse event: myalgia (44.7%), fatigue (44.5%), headache (37.7%), shivering (26.8%), fever (20.5%), and gastrointestinal symptoms (17.3%).

The incidence of solicited local and general symptoms was lower in subjects aged 70 years and older compared with those aged 50 to 69 years.

The majority of solicited local adverse reactions and general adverse events seen with Shingrix® had a median duration of 2 to 3 days.

Headache and shivering were reported more frequently by subjects after Dose 2 (28.2% and 21.4% respectively) compared with Dose 1 (24.4% and 13.8% respectively). Grade 3 solicited general adverse events (headache, shivering, myalgia and fatigue) were reported more frequently by subjects after Dose 2 (2.3%, 3.1%, 3.6% and 3.5% respectively) compared with Dose 1 (1.4%, 1.4%, 2.3% and 2.4% respectively).

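### The third ad hoc ISM trigger is contained in the second and adds no review; a cluster of non-serious Grade 3 related unexpected AEs sets off no automatic ISM review

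*Combined protocol and SAP*

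**What the plan says.** Section 12.8.2.2 names three events that call an ad hoc comprehensive ISM review without anyone having to ask for it:

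1. a death possibly or definitely related to the vaccine, which is also a hold rule;
2. "The occurrence of one study vaccine-related and unexpected SAE or Grade 4 AE", also a hold rule and repeated as such in section 11.5;
3. "The occurrence of a Grade 3 or higher vaccine-related and unexpected SAE in 2 or more of the study participants", which is not marked as a hold rule.

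The same section lets the Medical Monitor, the Protocol Chair or DAIT/NIAID ask for an ad hoc review. For planned reviews, section 12.8.2.1 states: "The Independent Safety Monitor shall review safety data at least yearly". Under section 12.8.1 the Medical Monitor and Project Manager "shall receive quarterly reports from the protocol investigator compiling new and accumulating information on AEs and SAEs". The 24-hour report in section 12.5.1 covers SAEs only.

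Two definitions matter. Under section 12.2.2 an event is unexpected if it is absent from the package insert or "is not listed at the specificity, severity or rate of occurrence that has been observed". Under section 12.2.3 seriousness depends on outcome, for example "Persistent or significant incapacity or substantial disruption of the ability to conduct normal life functions". Severity is graded separately, in section 12.3.1 and Appendices A to C.

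**The concern.** The third trigger asks for more events (two participants rather than one) and greater severity (Grade 3 or higher rather than any grade) than the second. Yet it carries the weaker consequence: a review with no hold. That ordering makes sense only if the third rule was meant for a less serious class of event than the second. As written it covers a narrower part of the same class.

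No SAE escapes review, because the second trigger is the stricter rule. What is at stake is the class that no trigger reaches: Grade 3 events that are related, unexpected and not serious. A cluster of these would appear in the quarterly reports to the Medical Monitor. It would come before the ISM only if someone chose to refer it, or at the planned review. Dose 2 is due at Day 60, and a three-month reporting interval is longer than that, so a cluster after dose 1 may first be reported when the affected participants have already had dose 2. Section 5.1 notes that "Grade 3 solicited general adverse events (headache, shivering, myalgia and fatigue) were reported more frequently by subjects after Dose 2".

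**Working it through.** The plan gives no operating figure for the triggers, so there is nothing to reproduce. The check has three steps.

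**Step 1: is the third trigger contained in the second?** Consider only related and unexpected events, and classify each by grade and seriousness. Grade 5 is death and always serious. That leaves nine types: non-serious Grades 1, 2, 3 and 4 (N1 to N4) and serious Grades 1 to 5 (S1 to S5). Two participants with one event each give 9 × 10 / 2 = 45 unordered pairs.

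- Second trigger: fires if either event is N4 or S1 to S5. It stays silent only when both events are among N1, N2 and N3, which is 3 × 4 / 2 = 6 pairs. It fires on 45 − 6 = 39.
- Third trigger: fires if both events are among S3, S4 and S5, which is 3 × 4 / 2 = 6 pairs. All 6 are among the 39.
- Pairs meeting the third but not the second: **0**. Pairs meeting the second but not the third: 39 − 6 = 33, so the subset is strict.

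A wider enumeration lets each event also be unrelated or expected. There are 5 × 2 × 2 × 2 − 4 = 36 event profiles (the 4 removed are non-serious Grade 5), hence 36² = 1,296 ordered pairs. Nine meet the third trigger and all nine meet the second. The result is the same whether the qualifiers related and unexpected apply to the Grade 4 AE in the second trigger or any Grade 4 AE counts.

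**Step 2: what is left uncovered, and what would AE in place of SAE add?** With that word changed, the third trigger fires if both events are among N3, N4, S3, S4 and S5, which is 5 × 6 / 2 = 15 pairs. Any pair containing N4, S3, S4 or S5 already meets the second trigger. Only N3 with N3 does not. The change adds exactly **1** pair: two participants, each with a non-serious Grade 3 event. As written, clusters of 2, 5, 10 or all 60 participants with such events meet none of the three triggers.

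**Step 3: how often might this arise?** The documents give no rate for non-serious Grade 3 related unexpected AEs, so the per-participant rate p is assumed. With 60 participants (section 13.1) and X ~ Binomial(60, p):

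P(X ≥ 2) = 1 − (1 − p)^60 − 60·p·(1 − p)^59

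For p = 0.01 this is 1 − 0.547 − 0.332 = 0.121.

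| Assumed p | Chance of at least 2 of 60 |
|---|---|
| 0.5% | 0.037 |
| 1% | 0.121 |
| 2% | 0.338 |
| 5% | 0.808 |
| 10% | 0.986 |

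The Grade 3 rates in section 5.1 (1.4% to 3.6% per dose for headache, shivering, myalgia and fatigue) concern known reactions, which are normally expected. They do not estimate p, and they make the lower rows more plausible. The same column shows how often the corrected trigger would call a review because of this class of event; the current text calls an automatic review for it with probability 0 at every rate.

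**The case against.** The strongest reply accepts the logic and disputes the weight. The redundancy removes no protection, since every SAE within the third trigger is caught earlier by a stricter rule. Nothing in the documents shows that AE was intended. The uncovered class is also narrow:

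- Some Grade 3 events will be serious under section 12.2.3, through the incapacity criterion or the important-medical-event criterion.
- For most systemic reactions in Appendix C an emergency visit or hospitalization is Grade 4, and Grade 3 redness in Appendix A can involve hospitalization, itself a seriousness criterion.
- The site should learn of severe reactions early. Participants are told to telephone about Grade 3 reactogenicity within a week (Appendix D), and the memory aid is reviewed at the visits in the week after each dose (section 8.4.1). Vaccine-related AEs go to VAERS (section 12.5.3).
- Once the Protocol Chair or DAIT/NIAID asks, the ISM will review.

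All of this stands and limits the practical weight. None of it supplies an automatic route to the ISM for Grade 3 events judged non-serious, and Grade 3 alone does not make an event serious.

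Two cautions about the correction also stand. The definition of unexpected includes rate of occurrence, so in a study of 60 some ordinary reactogenicity could be judged unexpected and prompt a review. And the corrected wording would not require the two events to be alike. Both could produce extra reviews, but neither leads to a hold.

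**Conclusion.** The point holds. As written, the third trigger in section 12.8.2.2 adds 0 of 45 possible event pairs to what the second already covers, and non-serious Grade 3 related unexpected AEs set off no automatic ISM review at any number of participants. This follows from the wording alone and assumes only that the word one in the second trigger means any such event, not just the first; the text does not limit it to the first. The probabilities rest on assumed rates and on independence between participants, and serve only as illustration. This should be corrected because a mandatory safety rule has no effect, but the consequence is modest: the vaccine is licensed, discretionary referral and quarterly Medical Monitor reports remain, and no endpoint or analysis changes.

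**What to change.** In the third trigger of section 12.8.2.2, replace the word SAE with AE and leave the rest of the sentence as it is. Keep the trigger as a review without a hold, and leave section 11.5 unchanged. Deleting the trigger would remove the redundancy but not the gap.

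The cost is a one-word protocol amendment and an occasional extra ISM review, with a chance of about 4% to 34% over the study at assumed rates of 0.5% to 2%. If such events were as common as 5% or 10% per participant, a review would be likely (81% and 99%).
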